8.1.4 Training of health providers on how to use ePOCT+

In intervention facilities, HCWs will participate in centralized in-person 3-day training course. They will receive general training on the epidemiology of diseases in Tanzania, the most important pediatric diseases and their clinical predictors, the content of the ePOCT+ algorithm and the importance of rational antibiotic and antimalarial use. General, key clinical skills will also be reviewed during this training and an introduction to the e-learning tool aimed at supporting these skills once they return to their facilities will be given. In addition, HCWs will receive training on how to use the ePOCT+ application on the tablet, using clinical case studies, as well as job aids for conducting and interpreting the results of POC tests which are not currently part of standard care at PHC level but are included in the algorithm (e.g. pulse oximetry and CRP rapid test).

During the month following this centralized training, HCWs will benefit from one visit for inservice face-to-face training during which trainers will accompany them in some of their consultations with real patients and help them optimize the way they use ePOCT+. Trainers will also support reorganization of workflows in the HF if necessary.

At the end of Phase 1, all HCWs from control HFs as well as those from the new participating facilities will receive the same training as described above. During both Phases 1 and 2, new personnel at study facilities will be trained through a dedicated module on the tablet and by their peers. This module will be available to all HCWs using ePOCT+ so that they can refresh their knowledge any time.

8.1.5 Supervision of health providers by the CHMT

The CHMT will be provided the medAL-monitor tool which is a dashboard available on PCs and tablets

allowing them to monitor indicators (see **Table 3**) related to pediatric consultations taking place in the HFs enrolled in the study. Data on the child's or the HCW's identification will not be provided, only the name of the heath facility will be available. Based on these indicators, the supervision team will be able to better organize on-site visits to HFs, prioritizing the lowest performing ones, knowing in advance what areas of improvement to concentrate on. As the persons in charge of HFs, as well as each HCW, will also have access to these indicators (fully anonymized except for their own data) to allow them to do self-auditing at HF level so that they are aware of their own performance in advance of receiving a CHMT supervision visit. The aim of the medAL-monitor tool is to stimulate HCWs' motivation and self-leadership to improve their skills and competencies, while enabling the supervision team to help them resolve remaining problems (Bessat et al. 2019).

8.1.6 Type of care, training and supervision provided at intervention and control facilities

In intervention HFs, HCWs will be guided by the ePOCT+ recommendations throughout the consultation. However, health care providers are ultimately responsible for the clinical management of all patients and may override recommendations of the algorithm and provide additional or withhold treatment according to their own clinical judgement. All concomitant diagnostic interventions and treatments will thus be left at the discretion of the provider but recorded in the ePOCT+ tool. In control HFs, routine care as currently implemented in Tanzanian primary care settings will be provided. Before the start of Phase 1, all skilled HCWs who are engaged in triage, assessment, and medical management of sick children in both intervention and control facilities will receive training in study-related procedures, including consent for electronic recording of data, and documentation of the final decision on referral, tests performed, final diagnoses and treatments using the tablet. In intervention HFs, training on the ePOCT+ tool will be provided as described above while in control facilities, standard paper guidelines (IMCI and Tanzanian national treatment guidelines) will be provided and HCWs reminded that these guidelines should be followed during patient management. They will also be informed that, after the end of phase 1, they will receive the intervention exactly as HCWs of initial intervention HFs did.

In intervention HFs, HCWs will receive feedback on the data registered through the ePOCT+ tool, and the CHMT will be using medAL-monitor to better target supervision and support to facilities. In control facilities, supervision by the district team will be done using the available DHIS2 data as usual.

In both intervention and control facilities, it is assumed that usual diagnostic tests and treatments will be provided through the routine health care system. Control HFs will not receive additional POC tests that HFs in Tanzania would not normally have available in similar settings (i.e. CRP test). Care for children under the age of five years is free of charge while caregivers are expected to pay out of pocket for health care expenses of older children (unless expenses are covered under an insurance policy). However, when not available at the HF, patients must procure their medications from nearby pharmacies or other HFs. To allow testing of the intervention under conditions as close as possible to those expected for future implementation, we will not provide routine diagnostics or medications in either intervention or control facilities. However, we will ensure that immediate life-saving treatments are available and will support the facility staff in managing stocks through routine mechanisms.

8.1.7 Measurement of primary and secondary outcomes

Data captured on the tablets used by health care workers during the consultation

During the pilot phase before Phase 1 begins, tablets will be provided to HCWs in both intervention and control HFs. In intervention HFs the tablets will contain the patient registration module followed

by the ePOCT+ algorithm that will guide them throughout the consultation process. In control HFs, tablets will only collect the patient demographics (see **Appendix 1**).

To determine the percentage of children prescribed an antibiotic or an antimalarial, as well as to know the final decision on referral and final diagnoses retained by HCWs, four questions will appear on the screen at the end of the consultation process, i.e. once the clinician has gone through the entire algorithm in intervention HFs or just after the patient registration module in control HFs. HCWs will be asked to document the final decision regarding the need for referral, tests performed and the results, decision on the date of follow-up (if needed), final diagnoses and final treatments prescribed. For each medicine prescribed, the dosage and duration of the treatment will also be recorded (see **Appendix 1**).

Data captured through phone calls or home visits (Phase 1) or automated phone calls or SMS (Phase 2) to caregivers

For Phase 1, research assistants will be trained to administer a simple questionnaire by phone to caregivers of all children at day 7 (range 6-14) after their initial consultation with a HCW of participating facilities, regardless of re-attendance visits. If the phone follow-up fails, up to four additional attempts will be made on the subsequent days, after which they will be deemed lost to follow-up. These research assistants will be placed outside HFs and blinded to which facility the child has attended as much as possible. Data recorded during these phone interviews will be collected electronically and sent at least once a day to the central server of the study at IHI. For the question related to the clinical primary outcome measure (percentage of children cured at day 7), field workers will be particularly trained not to influence caregivers when they answer the questions "Is the child cured?" and insist that they simply answer by "Yes" or "No". If the answer is "No", the caregiver will be strongly advised to re-attend a HF, if possible, the one they went to for the initial consultation. Same procedure will be implemented if home visits are required using a REDCap mobile application. The questions included in the phone questionnaire are listed in **Appendix 1**.

During Phase 2, instead of a phone call, caregivers will receive an automated SMS or automated phone call on day 7 with the same questions as in the questionnaire applied by phone. The automated follow-up system will be tested during Phase 1 in parallel with phone calls in a subset of patients, to check for congruency between the answers obtained by a caller and by automated voice message or SMS.

In Phases 1 and 2, when the participant reports that the family has no phone number, or no response is received from the phone call or SMS, the field assistant may make a physical follow up to ascertain the responses of several unanswered contact attempts with support of the local village leaders as key informants.

Data captured during the three cross-sectional quality of care surveys

Research clinical observers who have been trained on the study procedures will visit randomly selected HFs. They will ask HCWs present on that day for permission to observe a series of consecutive consultations. They will then ask the HCW to request oral permission from their patient and to sign a consent form indicating their own and the patient's consent to have an observer in the room. Observers will then record, using an electronic questionnaire, key symptoms (danger signs, main exposures and main symptoms) and signs (vital signs, main signs according to the child's main symptoms) assessed by HCWs, diagnostic tests requested, final decision on referral, final diagnoses retained, treatments prescribed and main information and advice given to caregivers. Observers will be trained not to interfere at all with the consultation process; only values of vital signs can be asked to the HCWs if necessary, to be recorded precisely by the observer.

8.1.8 Unique study identification number for each participant

Patients will be given a unique study identification number through a barcode or a QR code that will be placed into the patient paper medical record booklet. The ID identification labels

will be pre-printed in bulk (specific to the district and HF) and delivered to the facilities. The patient will also be given a card with information on the study and additional barcode stickers. The sticker will be scanned using a barcode/QR code reader in the tablet each time the child presents at a HF. In the registration module on the tablet, an advanced search system will be created that uses the study identification number, the name of the child, the name of the mother or father or caregiver and the date of birth, so that the child can be identified with certainty and former consultations, if any, can be retrieved, and linked to the new consultation. The same code will also be used in order to link the laboratory results from surveillance activities back to the child's consultation information.

8.2 Objective 2: Adapt the algorithm to epidemiological and demographic conditions

The algorithm will be improved in terms of diagnostic and prognostic accuracy and adapted to local fluctuations in epidemiology, demography, geography and resource availability. Each potential modification will first be evaluated by the Tanzanian clinical expert group for its clinical coherence, safety and potential benefit and then applied to the retrospective data. If these analyses confirm both a clinically relevant positive impact and estimate that there will be sufficient future cases during the study period to detect this improvement, the change in the algorithm will tested in a randomized substudy using the same study design as in Phase 1, except that randomization will take place at patient level rather than HF level. If the positive impact is confirmed in the sub-study, the modification will be implemented in all relevant locations/patient sub-groups. If the retrospective analyses confirm a positive and potentially clinically relevant impact of a modification where resource savings is also expected but there will not be sufficient power to formally test the change during the study period, the modification achieves the expected results given the accumulated data at the end of the study period, it will be retained.

During the sub-studies, HCWs attending a child who could potentially benefit from this modification in the algorithm will be informed about the potential change in the algorithm. Either the modified branch or the original branch of the algorithm will then randomly appear on the screen to guide the HCW's decisions. Antimicrobial prescriptions and clinical cure, as well as all the other available and outcome measures relevant for the algorithm change, will be assessed the same way as in Phase 1 and compared between children managed with the modified and the original version of ePOCT+. If the benefit is confirmed by the sub-study, the new algorithm branch will be implemented for all relevant children in the relevant HFs. If the benefit is not confirmed, the original version of the algorithm will be used in all involved children.

If shown to be promising according to the analyses of the retrospective data and considered feasible to implement, we will be testing modifications in the algorithm with a focus on the aims described below. Other types of modifications might also be tested if considered important by the clinical experts.

Adapting the frequency of mRDT testing to malaria prevalence:

As recommended by WHO (WHO 2011), in geographical areas where the positivity rate of malaria RDT is normally or seasonally falls below 1% (based on the data gathered through the use of ePOCT+), we will modify the "fever" branch of the algorithm to target malaria testing on the patient population at risk of having malaria. To do so, we will use the combination of demographic (e.g. village where the child lives), exposure (e.g. recent travel to an endemic area) and clinical (e.g. no other documented infection) criteria shown in the data analyses to best predict the presence of malaria. In this specific geographical area, we will thus randomize (at patient level) febrile children to be managed either using the original algorithm "fever" branch (that recommends all children to be tested for malaria), or using the modified version of the "fever" branch (that targets testing to the children at risk for malaria). If we measure that the clinical cure rate is equivalent to that of children managed with the original "fever" branch, the later will be implemented for all children in that geographical area. In

case the positivity rate would later increase in that area due to resurgence of malaria, the application would revert to the original "fever" branch until malaria prevalence goes down again.

This dynamic malaria testing strategy would reduce the number of malaria tests used (that would likely have been negative) and also increase the percentage of mRDTs that are positive, which will improve the motivation and trust of HCWs in malaria testing. This strategy has already been implemented in some areas or countries in Africa using malaria predictors described in the literature, but not yet based on individual patient local data as it will be done in the present study.

Improving the accuracy of pneumonia diagnosis:

The same study design as for malaria testing will be used to improve pneumonia diagnosis accuracy using a combination of clinical predictors or new diagnostic tools, and/or to save CRP rapid tests in children with cough or difficult breathing. The new "cough" branch of the algorithm will be implemented in all children either if the clinical cure rate with the new branch is expected to be better than that of children managed with the original "cough" branch OR if the number of CRP tests used is expected to decrease.

Assessing the utility of dengue rapid tests in outbreak conditions:

If the microbiological surveillance in a few sentinel sites (see chapter 8.3) identifies a dengue outbreak, a dengue rapid test will be added to the "unspecific fever" branch of the algorithm and tested using the same study design as above. The modified "unspecific fever" branch including dengue testing will be implemented in all children if the clinical cure rate with this new branch is better (i.e. >30% decrease in the clinical failure rate) than that of children managed with the original "unspecific fever" branch will revert to the original version and the use of dengue rapid tests will be stopped.

Assessing the utility of typhoid rapid tests in high prevalence conditions:

If the prevalence of typhoid in febrile children is shown to be >10% in a certain area or time period (based on the microbiological surveillance data), using rapid tests, even with sub-optimal sensitivity and specificity as it is the case for now, could be beneficial from a clinical point of view. Indeed, with a pre-test probability of 10% and a positive likelihood ratio of 4 for the typhoid RDT, the post-test probability is 30%. The performance of the test can be enhanced by adding clinical predictors identified in previous studies in Tanzania (De Santis et al. 2017).

In this situation, a typhoid rapid test will be added to the "unspecific fever" branch of the algorithm and its clinical utility assessed using the same design as above. The new "unspecific fever" branch including the typhoid rapid test would be implemented in all children of the high prevalence area, if the clinical cure rate with the new branch is better (i.e. >30% decrease in the clinical failure rate) than that of the original branch. When typhoid prevalence decreases, the "unspecific fever" branch will revert to its original version.

Improving prediction of a severe clinical outcome:

If a combination of demographic, clinical and/or laboratory predictors, or a new POC test, seems to allow for better identification of children who will develop severe disease and thus be hospitalized secondarily or die, the benefit of adding an alert to HCWs in the algorithm, recommending them to refer the child to hospital, will be evaluated. If adding this alert allows to decrease mortality by at least 10%, it will be implemented for all children.

Adapting the algorithm to improve cure rates of children with chronic disease risk factors:

If specific predictors of clinical failure can be identified in children with chronic disease risk factors (e.g. malnourished, HIV positive children, children with sickle cell disease), the relevant branches of the algorithm will be modified for these children (e.g. an antibiotic treatment may be recommended in a child with a certain clinical constellation). This personalized algorithm will be implemented in all children with the chronic disease risk factor if there is a clinical benefit as described above.

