10 STATISTICAL METHODS

10.1 Sample size calculations

Throughout the study, non-inferiority in clinical cure will be defined as a risk difference of <30% in the proportion of clinical failures while superiority in clinical cure will be defined as a decrease of \geq 30% in the proportion of clinical failures. Superiority regarding resources (whenever medicines prescribed or diagnostic tests ordered by HCWs or time spent to perform a consultation) will be defined as a decreased need of \geq 25%.

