10.1.2 Randomized sub-studies to test algorithm modifications (Phase 2)

Sample sizes for the randomized sub-studies aimed at evaluating the benefit of a modification in an algorithm branch will be calculated following the same general principles as for Phase 1. Consideration of the desired or acceptable difference in clinical cure rate will be determined according to the type of intervention applied. This acceptable difference cannot be decided prior to knowing what intervention will be implemented, and on which population or subpopulation this intervention will be applied. For example, a small improvement in the cure rate from 90% to 93% in a certain subpopulation of patients will be considered beneficial if not too demanding in terms of resources to be added. The same considerations will be applied for interventions aiming at improving the rational use of medicines (e.g. antibiotics or antimalarials). The highest sample size between that required for assessing the clinical outcome and that for the resource saving outcome will be used.

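### The Phase 2 rule for the cough branch lets an expected CRP saving justify adoption with no condition on cure, in conflict with the rest of the protocol

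*Protocol*

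**What the plan says.** Protocol 8.2, on pneumonia diagnosis, begins: "The same study design as for malaria testing will be used to improve pneumonia diagnosis accuracy". Saving CRP rapid tests in children with cough or difficult breathing is one of the stated aims. The text then gives this modification its own adoption rule, under which the new branch goes to all children when either of two criteria is met. The first concerns cure: "if the clinical cure rate with the new branch is expected to be better than that of children managed with the original". The second, which stands as a full alternative to the first, concerns only test use: "OR if the number of CRP tests used is expected to decrease".

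The malaria modification just above it also saves tests. Its condition for adoption, set against the existing fever algorithm, is: "If we measure that the clinical cure rate is equivalent to that of children managed with the original". For dengue the condition is "if the clinical cure rate with this new branch is better (i.e. >30% decrease in the clinical failure rate"), and typhoid follows the same pattern.

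General text also applies to Phase 2:

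- **8.2, opening.** Each modification "will first be evaluated by the Tanzanian clinical expert group for its clinical coherence, safety and potential benefit" and is then applied to retrospective data. Sub-studies compare cure between the two versions, and the original version stays if benefit is not confirmed.
- **3.2.** Modifications confirmed as safe and useful are implemented.
- **Synopsis, Objective 2 procedures.** Sub-studies of major changes assess benefit, harm or non-inferiority.
- **10.1.** For the whole study, "non-inferiority in clinical cure will be defined as a risk difference of <30% in the proportion of clinical failures". Resource superiority, which expressly covers diagnostic tests, is a reduction of at least 25%.
- **10.1.2.** "The highest sample size between that required for assessing the clinical outcome and that for the resource saving outcome will be used". The acceptable difference in cure is left open until the modification is known.
- **7.2.** A positive impact modification may raise cure, and/or save resources, and/or have another positive impact.

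**The concern.** The two cough criteria are alternatives, so the CRP criterion is enough by itself. It does not mention cure, does not say how large the saving must be, and turns on what is expected although a randomised comparison is to be run.

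Table 2 of the protocol gives CRP the role of targeting antibiotic prescription in children with respiratory symptoms. A branch that uses fewer CRP tests can therefore change who is treated, and cure is the outcome that would show whether this did harm. At stake is whether the measured cure result governs adoption. If the specific rule is applied as written, a sub-study could show more clinical failures and the branch would still satisfy its adoption criterion.

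**Working it through.** The plan gives no sample size, power or error rate for a cough sub-study, so there is no figure to reproduce. The check is mainly a comparison of texts.

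**Step 1. The six example modifications in 8.2.**

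| Modification | Condition for adoption |
|---|---|
| Malaria testing | measured equivalence of cure |
| Cough / pneumonia | better cure expected, or fewer CRP tests expected |
| Dengue test | more than 30% fall in failures |
| Typhoid test | more than 30% fall in failures |
| Severe-outcome alert | mortality down by at least 10% |
| Chronic risk factors | clinical benefit |

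Five of the six tie adoption to a clinical outcome. Only the cough rule has a route without one.

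**Step 2. Does the general text supply the missing condition?**

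- Expert review names safety but comes before the sub-study, so it cannot act on harm that the sub-study later shows.
- The requirement that benefit be confirmed does not say benefit in cure. Under 7.2, fewer CRP tests could be the confirmed benefit.
- The safe-and-useful sentence in 3.2 carries no margin. It follows directly on modifications aimed at health outcomes. Resource-saving modifications are dealt with earlier in 3.2, with no sub-study named.
- The 10.1 definitions would supply both limits, but the cough rule invokes neither, and 10.1.2 defers the cure difference.

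The general text therefore points towards a cure condition, while the specific rule omits it.

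**Step 3. Illustration of direction only.** Assumed inputs: individual randomisation; control failure 3% (the Phase 1 assumption in 10.1.1 for all sick children); CRP use falling from 40% to 30%, a relative fall of (40 − 30)/40 = 25%; 2,000, 5,640 or 8,000 children per arm; 200,000 simulated sub-studies per setting. The 5,640 is the unclustered Phase 1 size: 2 × 0.03 × 0.97 × (1.960 + 0.842)² / 0.009² ≈ 5,640. The literal rule adopts if either observed CRP use or observed failure is lower. The conditional rule requires lower observed CRP use and an upper 97.5% bound for the failure risk ratio below 1.3. That margin is borrowed from Phase 1 for illustration.

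| True failure risk ratio | Literal rule adopts | Conditional rule adopts (2,000 / 5,640 / 8,000) |
|---|---|---|
| 1.0 | about 100% | 30.8% / 68.7% / 83.0% |
| 1.3 | about 100% | 2.5% / 2.5% / 2.5% |
| 1.5 | about 100% | 0.23% / 0.02% / 0.01% |
| 2.0 | about 100% | about 0% throughout |

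Hand check at 5,640 and ratio 1.0: expected failures per arm are 169.2; SE of the log ratio = √[2 × (1/169.2 − 1/5,640)] = 0.107; ln 1.3 / 0.107 − 1.960 = 0.49; Φ(0.49) = 0.69, in agreement.

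The 100% column only restates the logic of a rule that ignores cure. The conditional column shows what a cure condition would do, and what it costs when cure is truly equal.

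**The case against.** The strongest reply is that the cough sentence should not be read alone. Section 8.2 itself requires safety review, a clinically relevant effect in retrospective data, a comparison of cure, and return to the original version if benefit is not confirmed. The 10.1 definitions apply throughout the study. Pneumonia is only an example to be explored, and 10.1.2 deliberately leaves the cure difference open until a modification is designed.

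Much of this stands, and it rules out three stronger readings that a reader might infer:

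- **That a harmful branch would be rolled out.** No text says the cough sentence overrides the general conditions, and those conditions could be invoked to stop it.
- **That the cure comparison has no role.** Section 8.2 and the synopsis require cure to be assessed in sub-studies. What is missing is a stated link from that result to this decision.
- **That a trivial CRP saving, such as 1%, is enough.** The 25% definition and the call for clinical relevance point the other way, although the cough rule cites neither.

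It also stands that the risk ratio of 1.3 belongs to Phase 1 (10.1.1) and should not simply be carried over.

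The reply does not remove the inconsistency. The safeguards set no cure limit that the cough rule invokes, and 7.2 accepts a resource saving alone. A team adopting this branch would naturally apply the rule written for it.

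**Conclusion.** The point holds as an internal conflict in the protocol. The CRP criterion for the cough branch has no cure condition and relies on expectation, against the malaria rule beside it, the general requirement of confirmed benefit and safety, and the 10.1 definitions. A branch with worse cure could be adopted under the rule as written; the documents do not establish that it would be.

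The size cannot be given as a probability, because the documents state neither a failure rate nor CRP use for children with cough. The simulation rests on assumed values and shows direction only. The scope is one of six example Phase 2 modifications. The Phase 1 cluster trial, its co-primary outcomes and the SAP are unaffected. The point should be corrected before any cough sub-study starts.

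**What to change.** Reconcile the cough rule in 8.2 with 3.2, 7.2, 10.1 and 10.1.2. The CRP criterion should apply only if both of these hold in the measured sub-study result:

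1. Cure is non-inferior to the original branch, by the 10.1 definition or by a margin fixed for that sub-study under 10.1.2 before it starts.
2. The CRP saving meets the 10.1 resource criterion of at least 25%.

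Replace expectation with the measured result in both limbs of the rule. State also whether the 25% is judged on the estimate or on a confidence bound.

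The cost is one sentence and a somewhat stricter rule. The cure data are already collected in the sub-studies. A cure condition lowers the chance of adopting a branch with truly equal cure if the sub-study is small (31% at 2,000 per arm against 83% at 8,000 in the illustration, before any 25% requirement). Section 10.1.2 already takes the larger of the clinical and resource sample sizes, so a sub-study sized that way for the chosen margin should carry this cost.
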